8.1.1. Severity Categorization

The severity of AEs must be recorded during the course of the event including the start and stop dates for each change in severity. An event that changes in severity should be captured as a new event. Worsening of pre-treatment events, after initiation of IP, must be recorded as new AEs (for example, if a subject experiences mild intermittent dyspepsia prior to dosing of IP, but the dyspepsia becomes severe and more frequent after first dose of IP has been administered, a new AE of severe dyspepsia [with the appropriate date of onset] is recorded on the appropriate CRF).

The Common Terminology Criteria for Adverse Events (CTCAE), Version 4.0 (Published: May 28, 2009 [v4.03: June 14, 2010]), should be referenced when assessing the severity of an AE. If an AE is not described in the CTCAE, the severity should be recorded based on the scale below:

Severity (Grade)	Definition
Mild (Grade 1)	A type of AE that is usually transient and may require only minimal treatment or therapeutic intervention. The event does not generally interfere with usual activities of daily living.
Moderate (Grade 2)	A type of AE that is usually alleviated with specific therapeutic intervention. The event interferes with usual activities of daily living, causing discomfort but poses no significant or permanent risk of harm to the research subject.
Severe (Grade 3)	A type of AE that interrupts usual activities of daily living, or significantly affects clinical status, or may require intensive therapeutic intervention.
Life-Threatening (Grade 4)	Life-threatening consequences; urgent intervention indicated.
Death (Grade 5)	Death related to AE

A life-threatening event (Grade 4 severity) is defined as an AE in which the subject was at risk of death at the time of the event; it does not refer to an event which hypothetically might have caused death if it was more severe (Section 8.2.3).

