8.1.7. Classification of Events as Pulmonary Exacerbations

The number of pulmonary exacerbations experienced by subjects will be assessed in this study. A pulmonary exacerbation will be defined as a new or change in antibiotic therapy (intravenous, inhaled, or oral) for a subject experiencing any 4 or more of the following signs or symptoms according to the modified Fuchs criteria presented by Ramsey et al.³⁷

- Change in sputum
- New or increased hemoptysis
- Increased cough
- Increased dyspnea
- Malaise, fatigue, or lethargy
- Temperature above 38°C
- Anorexia or weight loss
- Sinus pain or tenderness
- Change in sinus discharge
- Change in physical examination of the chest
- Decrease in pulmonary function by 10%
- Radiographic changes indicative of pulmonary infection

In addition to pulmonary exacerbations defined by the above criteria, physician-reported pulmonary exacerbations will also be recorded. Severity of pulmonary exacerbations will be scored according to the general principles described in Section 8.1.1.

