8.2.6. Serious Adverse Event Onset and Resolution Dates

The onset date of the SAE is defined as the date the event meets serious criteria. The resolution date is the date the event no longer meets serious criteria, the date the symptoms resolve, or the event is considered chronic. In the case of hospitalizations, the hospital admission and discharge dates are considered the onset and resolution dates, respectively.

In addition, any signs or symptoms experienced by the subject after signing the informed consent form, or leading up to the onset date of the SAE, or following the resolution date of the SAE, must be recorded as an AE, if appropriate.

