### 9.3 Adverse Events

Adverse events will be coded using the Medical Dictionary for Regulatory Activities (MedDRA) Version 23.1 to identify the system organ class and preferred term.

Treatment-emergent AEs are defined as events that are newly reported or reported to worsen in severity after the start of treatment. Adverse events that occur after the treatment start date, occur on the treatment start date with a time that is equal to or after treatment start time, or that have a missing AE start date will be categorized as treatment-emergent. Treatment-emergent AEs will be summarized for the safety analysis set.

For summaries of TEAEs by time interval, the categorizations for Part A will be: Overall, Study Day 1, 1 < Study Day ≤ 7, 1 ≤ Study Day ≤ 29, and Study Day > 29. The categorizations for Part B will be: Overall, Study Day 1, 1 < Study Day ≤ 7, 1 ≤ Study Day ≤ 36, 1 ≤ Study Day ≤ 57, and Study Day > 57. The categorizations for Part D will be: Overall, Study Day 1, 1 < Study Day ≤ 5, 1 ≤ Study Day ≤ 11, 1 ≤ Study Day ≤ 32, and Study Day > 32. The categorizations for the study overall will be: Overall, through 1 month post-dose (Day 29, Day 57, and Day 32 for Part A, Part B, and Part D, respectively), after 1 month post-dose (> Day 29, > Day 57, and > Day 32 for Part A, Part B, and Part D, respectively). Any TEAE with a completely missing start date will not be categorized into a specific time interval, but will be included in the Overall category.

Any dose limiting toxicities identified will be addressed in the clinical study report (CSR).

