### **9.3.2 Subject-level and Event-level Summary of AEs**

A summary table will be presented for each study part by dose group to reflect a count and percentage of subjects experiencing at least 1 TEAE in each system organ class and preferred term and a count of TEAEs occurring in subjects in the safety analysis set within each system organ class and preferred term. All percentages will use the number of subjects in the safety analysis set as the denominator. Therefore, if a subject has more than 1 AE within a system organ class, the subject will be counted only once in that system organ class. If a subject has more than 1 AE that codes to the same preferred term, the subject will be counted only once for that preferred term. For the event-level summaries, subjects experiencing more than 1 AE within a system organ class or preferred term will be counted more than once for that system

organ class or preferred term. Tabular summaries will be sorted by descending overall (MRT5005 + Placebo) frequency in subject counts by system organ class and by preferred term.

Using the same subject-level and event-level counting rules, a summary table of TEAEs by preferred term will be presented for the overall time period by dose group for each study part, as well as separately through Day 29, Day 57, and Day 32 for Part A, Part B, and Part D, respectively. In addition, the summary of AEs by preferred term will be presented for the study overall for the overall time interval and through 1 month post-dose (Day 29, Day 57, and Day 32 for Part A, Part B, and Part D, respectively) by pooled treatment group.

All AEs will be presented in data listings for subjects in the safety analysis set, including a flag to distinguish if the AE was treatment-emergent.

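### A severity change opens a new AE record that the SAP dates and counts on its own, so an easing pre-dose AE can become treatment-emergent and one continuing event can count several times

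*Protocol*

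**What the plan says.** **Recording.** Protocol 8.1.1 has sites record severity through the course of an event, "including the start and stop dates for each change in severity", and adds: "An event that changes in severity should be captured as a new event". Its next sentence deals with events already present before dosing: "Worsening of pre-treatment events, after initiation of IP, must be recorded as new AEs".

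**Treatment emergence.** SAP 9.3 begins with a definition: "Treatment-emergent AEs are defined as events that are newly reported or reported to worsen in severity after the start of treatment". The working rule comes next. "Adverse events that occur after the treatment start date" are treatment-emergent, as are those on the start date at or after the treatment start time and those with no start date. The working rule compares no severities.

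**Counting.** SAP 9.3.2 states: "For the event-level summaries, subjects experiencing more than 1 AE within a system organ class or preferred term will be counted more than once". SAP 9.4 applies the same rules to pulmonary exacerbations by time interval. The table footnotes define m as the number of adverse events and assign intervals by AE start day. Table 14.3.1.1 has event rows (all TEAEs, TEAEs by severity, TEAEs classified as exacerbations) separate from its subject rows. Tables 14.3.1.3 and 14.3.1.4 show events only.

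**Use.** Protocol 8.1.7 says "The number of pulmonary exacerbations experienced by subjects will be assessed in this study" and grades exacerbations by the principles of 8.1.1. Protocol 9.8.1 plans to analyze both their number and their incidence.

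**The concern.** The recording rule and the counting rule do not fit together. The first cuts one illness into segments, each with its own dates. The second treats each segment as an event that began on its own start date. There are two consequences.

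- **False treatment emergence.** A pre-dose AE that eases after dosing can acquire a record with a post-dose start. The date rule in SAP 9.3 then classes an improvement as a treatment-emergent event, although the definition just before it asks for a new or worsened event.
- **Multiple counting and late onset.** A continuing event whose severity changes adds one event per segment. If a change falls after an interval boundary, the event and its subject also appear in the later interval as a new onset.

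The frequency of TEAEs, including exacerbations, is part of the primary endpoint, and all analyses are descriptive. The tabulated counts are therefore the result itself, in active groups of 3 in Parts A and B.

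**Working it through.** The plan states no figure that bears on this point, so there is none to reproduce. The check applies the SAP's rules to example records. The days and grades are assumptions chosen for illustration.

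**Inputs**
- A new record for each severity change: Protocol 8.1.1.
- Treatment-emergent if the record starts at or after first dose: SAP 9.3, working rule.
- m = number of treatment-emergent records; n = number of distinct subjects with at least one: SAP 9.3.2 and table footnotes.
- Interval = start day of the record; Part A splits at Day 29: SAP 9.3 and table footnotes.
- Active group size 3 in Parts A and B: Protocol 9.6.

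**Comparison rule.** Linked segments form one event. It is treatment-emergent only if it began after dosing or if its post-dose severity exceeds its pre-dose severity.

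**Example 1: one Part A illness, mild from Day 20, moderate from Day 25, mild from Day 33**

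| | SAP rules | Linked |
|---|---|---|
| Overall | n = 1, m = 3 | n = 1, m = 1 |
| Days 1 to 29 | n = 1, m = 2 | n = 1, m = 1 |
| After Day 29 | n = 1, m = 1 | n = 0, m = 0 |
| Events by severity | 2 mild, 1 moderate | 1 moderate |

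In general, an illness with k severity segments gives m = k. The overall n does not change, but the late-interval n does.

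**Example 2: moderate from Day -5, easing to mild on Day 3**
- SAP date rule: the Day 3 record is post-dose, so 1 TEAE in 1 subject; 1/3 = 33.3% of an active group.
- Linked rule: severity did not rise, so 0/3 = 0%.

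**Example 3: mild from Day -5, becoming severe on Day 3**
- Both rules give 1 TEAE in 1 subject. A genuine worsening is classified correctly either way, so adding a worsening test loses nothing here.

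**Search for a linking rule.** The protocol, the SAP and the table and listing specifications contain no step that joins severity segments before counting or dating.

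**The case against.** **The pre-dose case rests on a reading.** For pre-treatment events, 8.1.1 expressly orders a new record only on worsening, its one example is a worsening, and the SAP definition would exclude an easing event. A careful site or programmer might never produce the false TEAE. This stands to the extent that the error can occur rather than must. However, the general sentence in 8.1.1 is not limited to worsening, and the rule a programmer would code looks only at dates.

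**Over-counting is the safer error in a first-in-human trial.** The SAP treats a missing start date as treatment-emergent, a missing relationship as related and a missing severity as severe. Those defaults cover unknown data, whereas here onset and severity are known. The argument does support leaving doubtful records unlinked.

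**Subject counts are the main display.** Protocol 9.8.1 specifies subjects with TEAEs, most AE tables print n (%) beside m, and every record is listed. This limits the damage. It does not reach the event-only tables, the late-interval n or the pre-dose case.

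**Stronger readings that the documents do not support**
- A reader might infer that every severity segment of an exacerbation will be tallied as an exacerbation. The documents do not say which segments carry that classification. The protocol definition needs new or changed antibiotics plus at least four signs or symptoms, which an easing segment may not meet.
- A reader might infer from Protocol 8.2.6 that an illness with a hospital stay counts three times. That section concerns signs and symptoms before the SAE "or following the resolution date of the SAE, must be recorded as an AE, if appropriate". It does not ask for the exacerbation itself to be entered three times, and the symptoms may code to other preferred terms.
- A reader might infer a bias between dose groups. Nothing in the documents shows that severity changes will differ by dose.

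**Conclusion.** The gap is real and should be closed before the final analyses. As written, the rules allow two errors. A pre-dose AE that eases after dosing can be flagged treatment-emergent, contrary to the SAP's own definition; one such case moves an active group of 3 from 0% to 33.3% for that term. One continuing AE or exacerbation can also add as many events as it has severity segments, and can place its event and subject in a later interval as a new onset. Whole-period subject counts for illnesses that begin after dosing are not inflated.

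This assumes that sites apply the general sentence of 8.1.1 to improvement as well as worsening, and that programmers apply the date rule of SAP 9.3 literally. For exacerbation counts it also assumes that more than one segment carries the classification. The documents give no rate of severity change, so the examples show what a single case does and not the expected total.

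**What to change.** Add to SAP 9.3:

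1. **Treatment emergence.** A record that continues a pre-dose AE is treatment-emergent only if its severity exceeds the last pre-dose severity. This reconciles the two sentences now there.
2. **Linking for event-level counts and interval tables only.** Join records when all of these hold: same subject and preferred term; different severity; the next record starts when the previous one stops, using times where collected; and the previous record is not recovered or resolved. The joined event takes the first onset and the maximum severity, and is serious if any segment is serious. For an event that began before dosing, date it from the first segment that qualifies under item 1, because its original onset precedes every interval.
3. **What stays separate.** Do not join records that resolved and recurred, including AEs after separate doses. Leave the febrile and hypersensitivity reaction counts and the 24-hour listings at record level. A looser join on adjacent dates would be unsafe. In Part D, pyrexia that resolved and returned on each of the five dosing days would collapse from 5 records to 1, although the SAP 9.4 febrile counts and the Part D stopping criterion (Protocol 4.5.5) depend on distinct occurrences.
4. **Transparency.** Keep every record in Listing 16.2.7.1.

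The cost is SAP wording and one derivation. Severity and outcome are recorded under Protocol 8.1.1 and 8.1.3, and the listing shells already carry AE start and end times, so no new data are needed. The downside is small: some links will need review where times or outcomes are missing, and records that cannot be linked stay separate by default.

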8.1.2. Relationship Categorization

Relationship of an AE or SAE to IP is to be determined by the Investigator based on the following definitions:

Relationship to IP	Definition
Not Related	Unrelated to IP.
Possibly Related	A clinical event or laboratory abnormality with a reasonable time sequence to administration of IP, but which could also be explained by concurrent disease or other drugs or chemicals.
Probably Related	A clinical event or laboratory abnormality with a reasonable time sequence to administration of IP, unlikely to be attributable to concurrent disease or other drugs and chemicals and which follows a clinically reasonable response on de-challenge. The association of the clinical event or laboratory abnormality must also have some biological plausibility, at least on theoretical grounds.
Definitely Related	The event follows a reasonable temporal sequence from administration of the IP, follows a known or suspected response pattern to the IP, is confirmed by improvement upon stopping the IP (de-challenge), and reappears upon repeated exposure (re-challenge). Note that this is not to be construed as requiring re-exposure of the subject to IP; however, the determination of definitely related can only be used when recurrence of the event is observed.

8.1.3. Outcome Categorization

The outcome of AEs must be recorded during the course of the study on the CRF. Outcomes are as follows:

- Fatal
- Not Recovered/Not Resolved
- Recovered/Resolved
- Recovered/Resolved with Sequelae
- Recovering/Resolving
- Unknown

8.1.4. Clinical Laboratory and Other Safety Evaluations

A change in the value of a clinical laboratory test, vital sign, ECG parameter, or other safety assessment (eg, oxygen saturation by pulse oximetry, spirometry testing, chest x-ray) can represent an AE if the change is clinically relevant or if, during treatment with the IP, a shift of a parameter is observed from a normal value to an abnormal value, or a further worsening of an already abnormal value. When evaluating such changes, the extent of deviation from the reference range, the duration until return to the reference range, either while continuing treatment or after the end of treatment with the IP, and the range of variation of the respective parameter within its reference range, must be taken into consideration.

If, at the end of the treatment phase, there are abnormal clinical laboratory, vital sign, or ECG values, or abnormal values in any other safety assessments which were not present at the pretreatment value observed closest to the start of study treatment, further investigations should be performed until the values return to within the reference range or until a plausible explanation (eg, concomitant disease) is found for the abnormal values.

The Investigator should decide, based on the above criteria and the clinical condition of a subject, whether a change in a clinical laboratory, vital sign or ECG parameter, or a change in any other safety assessment performed in the study is clinically significant and therefore represents an AE.

8.1.4.1. Evaluation of Elevations in Liver Function Tests

Subjects meeting any of the 3 criteria listed below must be followed closely with repeat confirmatory testing within 48 to 72 hours of the initial finding (should include ALT, AST, ALP, GGT, INR, and total bilirubin testing) to determine if these parameters are increasing or decreasing. Subjects should be followed closely for clinical progression and there should be monitoring of ALT, AST, ALP, GGT, INR, and total bilirubin levels, as clinically indicated. Subjects should be followed until their transaminases and other laboratory parameters normalize or return to baseline.

- Elevation of ALT or AST to >5 x ULN in a subject regardless of baseline value
- Elevation of ALT or AST to >3 x ULN in a subject with a normal baseline or elevation of >3 x ULN from the subject's actual baseline if not normal, with the appearance of fatigue, nausea, vomiting, right upper quadrant pain or tenderness, fever, rash, and/or eosinophilia ($>5\%$).
- Elevation of ALT or AST to >3 x ULN in a subject with a normal baseline or elevation of >3 x ULN from the subject's actual baseline if not normal, and total bilirubin >2 x ULN or INR >1.5 .

If any of the above criteria is met by a Part B or Part D subject who has not completed dosing with IP, treatment must be interrupted immediately and the Medical Monitor notified of this action.

A thorough investigation of other potential causes should be conducted in all cases. If no convincing alternative etiology (eg, pre-existing CF-related liver disease, viral hepatitis, alcohol ingestion, concomitant medication [such as antibiotic treatment]) for the elevated transaminases and symptoms is identified, regardless of whether ALT or AST levels have improved, treatment of the subject must be discontinued, in consultation with the Medical Monitor. If a convincing alternative etiology for the elevated transaminases is identified and the subject's symptoms and laboratory findings have improved, the Investigator may consider resuming IP treatment with close monitoring, in consultation with the Medical Monitor.

8.1.4.2. Development of Immune Responses to CFTR Protein or PEG

In addition to the time points specified in the schedule of assessments, immunogenicity testing will also be performed when immunogenicity is suspected, such as allergy/hypersensitivity events or unexplained bronchospasm.

8.1.5. Pregnancy

All pregnancies are to be reported from the time the subject signs the informed consent until the final study visit on Day 337 (± 3 days) in Part A, Day 365 (± 3 days) in Part B, or Day 341 (± 3 days) in Part D of the study.

Any report of pregnancy for any female study participant or the partner of a male study participant must be reported within 24 hours to Rho Product Safety. The pregnancy report and any applicable follow-up information will also be sent to the Medical Monitor by Rho Product Safety. The pregnant female study participant must be withdrawn from the study.

Every effort should be made to gather information regarding the pregnancy outcome and condition of the infant. It is the responsibility of the Investigator to obtain this information within 30 calendar days after the initial notification and approximately 30 calendar days postpartum.

Pregnancy complications such as spontaneous abortion/miscarriage or congenital abnormality are considered SAEs and must be reported to Rho Product Safety (Section 8.2.2). Note: An elective abortion for non-medical reasons is not considered an SAE.

In addition to the above, if the Investigator determines that the pregnancy complication meets serious criteria, it must be reported as an SAE to Rho Product Safety (Section 8.2.2). The test date of the first positive serum β -hCG test or ultrasound result will determine the pregnancy onset date.

8.1.6. Abuse, Misuse, Overdose, and Medication Error

Abuse, misuse, overdose, or medication error (as defined below) must be reported to the Sponsor according to the SAE reporting procedure whether or not they result in an AE/SAE as described in Section 8.2. Note: The 24-hour reporting requirement for SAEs does not apply to reports of abuse, misuse, overdose, or medication errors unless these result in an SAE.

The categories below are not mutually exclusive; the event can meet more than 1 category.

- **Abuse** – Persistent or sporadic intentional intake of IP when used for a non-medical purpose (eg, to alter one's state of consciousness or get high) in a manner that may be detrimental to the individual and/or society
- **Misuse** – Intentional use of IP other than as directed or indicated at any dose (Note: this includes a situation where the IP is not used as directed at the dose prescribed by the protocol)
- **Overdose** – Intentional or unintentional intake of a dose of IP higher than the protocol-prescribed dose
- **Medication Error** – An error made in prescribing, dispensing, administration, and/or use of an IP. For studies, medication errors are reportable to the Sponsor only as defined below.

Medication errors should be collected/reported for all products under investigation.

The administration and/or use of the unassigned treatment is/are always reportable as a medication error.

The administration and/or use of an expired IP should be considered as a reportable medication error.

